Project title: “A Phase II Therapeutic Trial of the Use of Dabrafenib and Trametinib in Patients with BRAF V600E Mutation Positive Lesions in Erdheim Chester Disease”.

Draft/version number: 03-June-2014 / Version 1

Draft/version number: 16-July-2014/ Version 2

Draft/version number: 05-September-2014/Version 3

Draft/version number: 07-November-2014/Version 4; Amendment #1-A

Draft/version number: 26-March-2015/Version 5; Amendment #2-B

Draft/version number: 14-December-2015/Version 6; Amendment #3-C

Draft/version number: 26-January-2016/Version 7; Amendment #4-D

Draft/version number: 22-August-2016/Version 8; Amendment #5-E

Draft/version number: 17-Janaury-2017/Version 8; Update to Amendment #5-E

Draft/version number: 03-March-2017/Version 9; Amendment # 6-F (CTEP: Amendment #11)

Draft/version number: 16-June-2017/Version 10; Triennial Review

Draft/version number: 11-July-2017/Version 11; Problem 6 response and amendment.

NHGRI Protocol Number: 15-HG-0006

Principal Investigator: [name]. PhD

Title/Section/Branch/Institute: Clinical Director/Office of the Clinical Director/National Human Genome Research Institute.

IND/IDE reference number: CTEP Drugs

Collaborating Institutions: NCI; CTEP

Protocol Summary

Full Title:	“A Phase II Therapeutic Trial of the Use of Dabrafenib and Trametinib in Patients with BRAF V600E Mutation Positive Lesions in Erdheim Chester Disease”.
Principal Investigator:	[name], PhD, Medical Genetics Branch, NHGRI
Sample Size:	N= 18
Accrual Ceiling:	18
Study Population:	Individuals with documented Erdheim-Chester Disease
Accrual Period:	January 2015 – January 2019
Study Design:	In this phase II open-label clinical trial, we clinically evaluate ECD patients with the BRAFV600E mutation and administer combination therapy with dabrafenib, a BRAFV600E inhibitor, and trametinib, an inhibitor of MEK, downstream of BRAF. We will determine the safety, tolerability, and efficacy of dabrafenib and trametinib in patients with ECD who harbor the BRAFV600E mutation. Patients are seen at 1 week, 1 month, 2 months, 4 months, and 6 months, 8 months, 10 months and 12 months to complete one year of therapy and off therapy follow ups will happen at 15 months, 18 months and 24 months to complete a 2-year trial. Target lesions will be assessed using RECIS criteria.
Study Duration:	Start Date: January 2015. End Date: January 2019.
Primary Objective:	To determine the safety, efficacy, and response rate of the combination of dabrafenib and trametinib in ECD.
Secondary Objectives:	Determine the time response, survival, and resistance to therapy.
Exploratory Objectives:	To monitor involvement and progression of disease and duration of treatment efficacy.
Endpoints:	The endpoint for an individual is reduction in target lesion size by RECIS criteria. For the trial, it is partial or complete response of at least 3 of the first 6 patients.

Contents

Protocol Summary	2
List of Abbreviations	4
1.0 Precis	5
2.0 Objectives and specific aims.....	6
3.0 Brief rationale and background.....	6
4.0 Description of study design	13
5.0 Description of procedures:	13
6.0 Description of study population	52
7.0 Description of study statistical considerations and/or analytic plan:.....	60
8.0 Description of potential benefits of study:	64
9.0 Description of likelihood and seriousness of harms and how safety will be maximized:	64
10.0 Description of how privacy and confidentiality of medical information/biological specimens will be maximized.....	71
11.0 Assessment of risk/benefit ratio	71
12.0 Unanticipated Problems: Collection, monitoring, analysis and reporting of adverse events and protocol deviations	73
13.0 Description of alternatives to participation	73
14.0 Description of consent process	74
15.0 Description of any financial compensation	75
16.0 References	75

List of Abbreviations

AE	Adverse Event/Adverse Experience
CLIA	Clinical Laboratory Improvement Amendment of 1988
COI	Conflict of Interest
DHHS	Department of Health and Human Services
DSMB	Data Safety and Monitoring Board
GCP	Good Clinical Practice
ICF	Informed Consent Form
IRB	Institutional Review Board
N	Number (typically refers to number of subjects/sample size)
NHGRI	National Human Genome Research Institute, NIH
NIH	National Institutes of Health
OHRP	Office for Human Research Protections
OHSRP	Office of Human Subjects Research Program
PI	Principal Investigator
PK	Pharmacokinetics
QA	Quality Assurance
QC	Quality Control
SAE	Serious Adverse Event/Serious Adverse Experience
SOP	Standard Operating Procedure
UP	Unanticipated Problem
WES	Whole Exome Sequencing
WGS	Whole Genome Sequencing

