The study will be conducted as an optimal Simon two-stage phase II trial in order to rule out an unacceptably low 10% clinical response rate (PR+CR: $p_0=0.10$) in favor of a targeted rate consistent with 40% ($p_1=0.40$). Maximum trial size would be set at 18 evaluable patients. If at least 4 responses (at least 22%) were observed among the 18 evaluable patients, this regimen would be considered worthy of further testing in this disease. If no responses were observed among the initial 6 patients, the study would be terminated early and declared negative. This design yields at least 90% power to detect a true response rate of at least 40%. It yields at least .90 probability of a negative result if the true response rate is no more than 10%, with at least .59 probability of early negative stopping. A temporary pause in the accrual to the trial may be necessary to ensure that enrollment to the second stage is warranted.

To ensure safety and feasibility of the selected dose for patients with ECD, we will assess the toxicity profile and dose delivery after the first 6 subjects have completed 3 months of therapy. If 3 or more individuals do not take at least 80% of the full doses of both drugs over 3 months due to dose modification for toxicity, revision of the dose schedule should be considered. Safety will be monitored on a continuous basis and feasibility of drug administration will be reviewed after 12 patients and then 18 patients have completed the 3 months of therapy.

All patients who receive any amount of the study drug will be evaluable for toxicity. Toxicity and doses adjustment will be perform as per the guidelines discussed on sessions 4.7 and 9 where dosing modifications and adverse events are discussed. Reassessment of the dose-schedule when 3 months or 12 cycles of therapy are completed will be performed by collecting the patient's medication diary information. This information will be collected by the study PI or the study coordinator by direct communication with the patient.

Besides response measured through imaging studies, physical and emotional well-being will be evaluated to assess improvement in daily living as exploratory endpoints. These

evaluations will be performed by the rehabilitation medicine and pain and palliative care teams during the treatment part of this trial as well as the off therapy follow up period. The list of tools and evaluations is available on sections 4.1.2 and 11.3.

7.1.2- Stratification Factors

N/A

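### The Protocol Summary's trial-level criterion (at least 3 responders in the first 6 patients) contradicts the Simon rule in Section 7.1.1 (at least 4 of 18) and has only 46% power at the target rate

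*Combined protocol and SAP*

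**What the plan says.** The Endpoints row of the Protocol Summary first gives an individual endpoint (reduction in target lesion size) and then a trial-level one: "For the trial, it is partial or complete response of at least 3 of the first 6 patients". The same Summary gives a sample size and accrual ceiling of 18.

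Section 7.1.1 (Study Design/Endpoints) describes an optimal Simon two-stage trial with a null response rate (PR+CR) of 10% and a target of 40%. On size: "Maximum trial size would be set at 18 evaluable patients". On the first six patients: "If no responses were observed among the initial 6 patients, the study would be terminated early and declared negative". On the final verdict: "If at least 4 responses (at least 22%) were observed among the 18 evaluable patients, this regimen would be considered worthy of further testing". It claims at least 90% power at a 40% rate, at least .90 probability of a negative result at 10%, and at least .59 probability of early negative stopping.

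Section 7.1.1 also contains a threshold of 3 or more among the first 6 patients, but that one counts patients who do not take at least 80% of full doses over 3 months. It concerns dose delivery, not response.

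**The concern.** The two statements concern the same outcome, PR or CR, which carries the primary response-rate objective. They differ in the threshold (3 or 4), the denominator (6 or 18) and the job given to the first six patients (the verdict, or a futility screen only).

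The same data can therefore be called positive under one rule and negative under the other:

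- 2 responders in the first 6 and 5 in 18: fails the Summary, succeeds in 7.1.1.
- 3 responders in the first 6 and 3 in 18: succeeds in the Summary, fails in 7.1.1. This direction is rare.

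In a single-arm, open-label trial of 18 patients, the prespecified decision rule is the main protection against choosing the conclusion after the data are seen. Two rules for one outcome weaken that protection.

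**Working it through.** **Inputs.** From 7.1.1: p0 = 0.10, p1 = 0.40, n1 = 6, stop if 0 respond, n = 18, positive if at least 4 respond. From the Summary: positive if at least 3 of the first 6 respond. Responses are treated as independent with a common probability p.

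**Step 1. Reproduce the 7.1.1 figures.** With X1 ~ Bin(6, p) and X2 ~ Bin(12, p),

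P(positive) = Σ over x = 1..6 of P(X1 = x) · P(X2 ≥ 4 − x).

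| Term | p = 0.40 | p = 0.10 |
|---|---|---|
| x = 1: P(X1=1)·P(X2≥3) | 0.1866 × 0.9166 = 0.1711 | 0.3543 × 0.1109 = 0.0393 |
| x = 2: P(X1=2)·P(X2≥2) | 0.3110 × 0.9804 = 0.3049 | 0.0984 × 0.3410 = 0.0336 |
| x = 3: P(X1=3)·P(X2≥1) | 0.2765 × 0.9978 = 0.2759 | 0.0146 × 0.7176 = 0.0105 |
| x ≥ 4: P(X1≥4) | 0.1792 | 0.0013 |
| **Total** | **0.931** | **0.085** |

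Power is 93.1% and the probability of a negative result at 10% is 1 − 0.085 = 0.915. Both stated bounds (at least 90% and at least .90) are met.

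**Step 2. The Summary rule.** P(X1 ≥ 3):

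- p = 0.40: 0.27648 + 0.13824 + 0.036864 + 0.004096 = 0.4557
- p = 0.10: 0.01458 + 0.001215 + 0.000054 + 0.000001 = 0.0159

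**Step 3. How often the verdicts conflict.** The 7.1.1 rule is positive and the Summary negative exactly in the x = 1 and x = 2 rows above. The reverse needs 3 responders in the first 6 and none in the next 12.

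| | p = 0.40 | p = 0.10 |
|---|---|---|
| 7.1.1 positive, Summary negative | 0.4760 | 0.0728 |
| Summary positive, 7.1.1 negative | 0.27648 × 0.6^12 = 0.0006 | 0.01458 × 0.9^12 = 0.0041 |
| **Opposite verdicts** | **0.477** | **0.077** |

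**Step 4. Try to reconcile them.** Suppose 3 of 6 is only a gate to the second stage, followed by at least 4 of 18. Keeping the x = 3 and x ≥ 4 rows, power is 0.2759 + 0.1792 = 0.455 and type I error is 0.0105 + 0.0013 = 0.012. That is far below the stated 90% power, and it contradicts the 7.1.1 instruction to stop only on zero responses. Reading 3 of 6 as an early claim of efficacy also fails, because 7.1.1 has no early positive stop.

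**The case against.** The strongest reply is that the Summary is only a synopsis. Section 7.1.1 is the one place with a named design, hypotheses, a stopping rule and operating characteristics, so a reader has good grounds to treat it as governing. On that view the defect is a misstated synopsis, not a missing plan. This has weight, but the document states no order of precedence. Section 4.0 sends the reader for the full design and statistical description to Sections 5.6.1 and 9, which cover the study agents and harms, so the document's own pointer does not lead to the Simon rule.

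The Summary also says endpoint, not success, and gives no hypotheses or power of its own. The 46% therefore comes from applying the 7.1.1 rates to it. That is fair to note, but a responder count stated for the trial, separately from the individual endpoint, has no natural meaning except as a decision rule, and 40% is the protocol's own target. The conflict does depend on the true rate: it is 7.7% at 0.10, 32.6% at 0.50, 17.5% at 0.60 and 7.0% at 0.70. The contradiction itself needs no power figure.

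Finally, the dose-delivery trigger in 7.1.1 may be where the 3-of-6 wording came from, but nothing in the document shows this and the finding does not rest on it.

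**Conclusion.** The point holds. The document carries two incompatible trial-level criteria for the primary response outcome, and no reading of the Summary sentence makes it agree with Section 7.1.1. If the true response rate is 40%, the Summary rule has 45.6% power against 93.1% for the 7.1.1 rule, and the verdicts conflict in 47.7% of trials (47.6% positive only under 7.1.1, 0.06% the reverse). At 10% the type I errors are 1.6% and 8.5%.

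These figures assume independent responses with a common rate, and 18 evaluable patients whenever the trial continues past stage 1. Because a decision threshold is wrong as written and the primary conclusion can flip on it, this must be corrected, even though the fully specified rule is easy to identify.

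**What to change.** Replace the trial-level sentence in the Summary's Endpoints row with the 7.1.1 rule, for example: *The trial stops and is negative if none of the first 6 evaluable patients has a CR or PR. Otherwise accrual continues to 18 evaluable patients, and the regimen merits further study if at least 4 of the 18 have a CR or PR.* Delete the 3-of-6 criterion.

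Patients are already enrolled (end of Section 3.1) and the 7.1.1 rule is the more lenient of the two, so record the change as a dated correction of the Summary, with its reason, rather than as a new rule.

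Before copying the first-stage size, settle a separate discrepancy in 7.1.1. The stated early-stopping probability of at least .59 fits 5 first-stage patients (0.9^5 = 0.590), not 6 (0.9^6 = 0.531). The power and negative-result claims hold with 6, so this does not affect the choice between the two rules. The section pointer in 4.0 can be corrected in the same amendment.

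The cost is one sentence in the Summary and a short amendment note, with no added patients, procedures or analyses.

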1.0 Precis

Erdheim-Chester Diseases (ECD) is a very rare non-Langerhans cell histiocytosis of unknown origin and pathogenesis. It has been reported mainly in adult males over the age of 40 years, although cases have been reported in females as well. Children are rarely affected. Mutation of the BRAF gene, specifically BRAFV600E, has been recently identified in 50% of Erdheim Chester lesions in a French cohort. This somatic mutation is believed to be the driver mutation in positive cases. Other genes that are involved in this disease process include NRAS, MAP2K1, PIK3CA, ARAF and other genes of the RAS pathway that are currently being studied. The clinical characteristics of ECD range from asymptomatic to multisystemic involvement; longitudinal progression and natural history are becoming better understood. ECD commonly affects the bones, kidneys, retroperitoneal space, skin and brain. If untreated, the disease progresses rapidly, causing fatal outcomes due to severe lung disease, chronic renal failure, cardiomyopathy and other complications. The diagnosis of ECD relies upon imaging studies and specific pathologic findings in biopsies of affected organs, i.e., fibrosis and infiltration of tissues with foamy histiocytes, lymphocytes, and plasma cells. Immunohistochemistry reveals cells positive for CD68 and CD163 and negative for CD1a, with 20% positivity to S-100. There is no standard treatment for ECD, although chemotherapy, radiation, stem cell transplantation, alpha-interferon, anakinra, imatinib and sirolimus have been proposed. The recent discovery of the BRAFV600E mutation in several ECD patients has opened a new area for treatment options. Vemurafenib, an FDA approved BRAF inhibitor for the treatment of patients with metastatic or unresectable melanoma with the V600E mutation, binds to this form of mutated BRAF causing protein inactivation. The use of vemurafenib in patients with ECD has been reported in 3 patients who experienced remission of the disease, and is currently being studied in the U.S. and Europe as monotherapy. Tumor/disease resistance to vemurafenib has occurred in melanoma and other cancers, although it has not been reported in patients with ECD. In this protocol, we propose to clinically evaluate ECD patients with the BRAFV600E mutation and administer combination therapy with dabrafenib, a BRAFV600E inhibitor, and trametinib, an inhibitor of MEK, downstream of BRAF. Screening for possible contraindications will be made prior to the administration of the first dose. With this trial, we will determine the safety, tolerability, and efficacy of dabrafenib and trametinib in patients with ECD who harbor the BRAFV600E mutation. Dabrafenib (which initial dose was 150mg BID, but due to high frequency pyrexia the dose was changed to 100mg BID for patients enrolled after amendment #6 of 12/27/2015) at a dose of 100mg will be given twice daily p.o.; trametinib 2mg will be given once daily p.o. Patients will be seen at 1 week, 1 month, 2 months, 4 months, and 6 months, 8 months, 10 months and 12 months to complete one year of therapy and off therapy follow ups will occur at 15 months, 18 months and 24 months to complete a 2 year trial.

2.0 Objectives and specific aims

2.1 Primary Objectives

2.1.1 - To study the efficacy and safety of dabrafenib and trametinib as combination therapy in patients with BRAFV600E positive Erdheim Chester Disease.

2.1.2 - To determine the clinical response rate to dabrafenib and trametinib combination therapy in patients with BRAFV600E positive Erdheim Chester Disease.

2.2 Secondary Objectives

2.2.1 - To determine time response, progression free survival and overall survival.

2.2.2 - To assess disease resistance to this combination therapy.

2.3 Exploratory Objectives:

2.3.1 - To monitor the degree of histiocytic infiltration-fibrosis progression, stability and regression under combination therapy using FDG-PET scan, MRI scans, CT scans and T-99m bone scans.

2.3.2 - To monitor serum CRP, ESR, and cytokine levels as inflammatory markers prior to and during combination therapy.

2.3.3 - To monitor renal function prior to and during combination therapy in order to assess for functional improvement.

2.3.4 - To evaluate the level of functioning, fatigue, motor skills and ability to perform routine daily activities prior to and during therapy in order to assess for improvements in these areas as well as quality of life improvement.

2.3.5 - To establish duration of treatment-endpoints in patients with BRAF V600E positive ECD lesions.

3.0 Brief rationale and background

3.1 Study Diseases:

The histiocytoses are a unique group of disorders with varied clinical presentations and outcomes. These disorders generally present in childhood; a recently increased frequency in adults reflects more accurate diagnosis in that age group. The histiocytoses cannot be categorized as entirely genetic, neoplastic, or reactive, and the pathophysiology remains poorly understood. For histiocytoses such as Langerhans cell histiocytosis and familial hemophagocytic lymphohistiocytosis, certain genetic associations have been made²⁷. In addition, clonality has been proven for Langerhans cell histiocytosis, but not for other types of histiocytosis such as Rosai Dorfman disease, which involves the lymph nodes and sinuses. Because of the rarity of histiocytoses, clinical and basic research dedicated to these disorders has been insufficient. The histiocytoses have been divided into Langerhans cell

or non-Langerhans cell subtypes, with dendritic, macrophage/monocytic, and malignant forms²⁷.

The clinical presentation, progression, response to therapy and outcome varies in each of the different histiocytoses^{12,18,23,27}. Patients can present with no symptoms, in which case the disease is diagnosed incidentally based upon involvement of a single organ system, or they can present with multisystem disease causing organ failure. Some patients with Rosai-Dorfman and juvenile xanthogranuloma may have a benign course or even exhibit regression without symptoms, while other patients progress to a complex multiorgan disease. Those histiocytoses classified as malignant generally prove fatal without treatment, and may progress even with treatment²⁷.

Erdheim Chester disease (ECD), first described in 1930¹², is a type of non-Langerhans cell histiocytosis that can present with no symptoms or only bone pain and fatigue, but can also present with multisystem involvement causing one or more of the following: cerebellar syndrome, panhypopituitarism, lung and cardiac disease, renal failure, bone disease and retroperitoneal fibrosis^{18,29,38}. ECD is not considered a cancer, although recent findings of BRAF gene mutations suggest that ECD might represent a low-grade malignancy¹⁹. Its etiology and pathogenesis remain areas under active investigation. Animal models, cell lines and affected families are limited due to the rarity and sporadic nature of the cases. In fact, there have never been two patients in the same family with ECD.

ECD has been reported mainly in adult males over the age of 40 years, although females can be affected as well. Children are rarely affected. The pathophysiology of ECD has not been determined, but the disease results in part from an increased inflammatory response and intense immune activation. The principal players include interferon alpha, interleukin 1/interleukin 1 receptor antagonist, interleukin 6, interleukin 12 and monocyte chemotactic protein 1, indicating a Th-1 oriented systemic immune disturbance^{3,18}. A mutation in the BRAF gene, BRAFV600E, has been recently identified in 50% of ECD lesions in a French cohort, with verification in U.S. patients¹⁹. Other genes that are involved in this disease process include NRAS, MAP2K1, PIK3CA, ARAF and other genes of the RAS pathway that are currently being studied. This somatic mutation may be responsible for the histiocytic infiltrations seen in ECD. The clinical characteristics of ECD range from asymptomatic to multi-systemic involvement. After diagnosis, ECD progresses rapidly, causing fatal outcomes due to severe lung disease, chronic renal failure, cardiomyopathy and other complications if left untreated. The diagnosis of ECD relies upon imaging studies and specific pathologic findings in biopsies of affected organs, i.e., fibrosis and infiltration of the affected tissues with foamy histiocytes, lymphocytes, and plasma cells. Immunohistochemistry reveals cells positive for CD68/CD163 and negative for CD1a; there is 20% positivity for S-100^{17,18,27}.

The natural history of ECD is still under investigation. Past literature describes the disorder as a condition that mainly affects males. The average age at diagnosis is 53 years and death from the disease occurs approximately 3 years after diagnosis. The typical presentation involves lower extremity bone pain, polyuria, polydipsia, fatigue and other nonspecific findings. Clinical evaluations reveal renal failure and inflammation with elevated CRP. Imaging studies show osteosclerosis, a “hairy” appearance to the kidney, and coated aorta on CT scan of the abdomen. Pituitary imaging usually shows a thickened pituitary stalk associated with signs and symptoms of diabetes insipidus and other hormonal disturbances. The differential diagnosis includes Paget’s disease of the bone, lymphoma, pituitary adenoma, and granulomatous disorders. ECD can also be confused with adult onset storage disorders such as Gaucher disease and Fabry disease¹². Pathology can be inconclusive; patients often remain undiagnosed and are treated empirically with steroids or chemotherapy.

In the past decade, the natural history of ECD has become better understood, with more than 400 cases reported since 1930. The first sign of ECD varies widely, since patients can present with many manifestations or be diagnosed incidentally. Increased awareness and research has increased the number of reported cases and shortened the time between presentation and diagnoses from up to 10 years to months or weeks, depending upon the medical institution involved. The frequency of the main manifestations varies from patient to patient. In our experience at the NIH with 32 patients, bone involvement, diabetes insipidus, retroperitoneal fibrosis and CNS disease are among the most common manifestations. Age at diagnosis ranges between 19 and 68 years. The average age of disease onset or first signs and symptoms is in the early thirties.

Diagnostic criteria for ECD have not been established, but the association of the pathological findings with elevated CRP, retroperitoneal fibrosis, pituitary stalk involvement and T-99m bone scan showing increased radiotracer uptake in the long bones are highly suggestive of ECD¹⁸. Pathology along with a positive bone scan can establish the diagnosis.

There is no standard treatment for ECD. Since the exact etiology is not known, there are no approved drugs for this condition. Patients have been treated empirically with interferon alpha (3-9 million units; 135mcgr pegylated form) weekly or high dose (>18 million units; >180mcgr pegylated form), anakinra (100mg SC daily), imatinib (400mg daily), steroids, and chemotherapy such as cladribine given in 6 cycles. Less frequently used drugs include rapamycin, tocilizumab and infliximab. No clinical trials have been performed to assess the safety and efficacy of these medications; their use is anecdotal, patient therapy is modified on an individual basis, and the results are not promising. Patients with CNS disease are the group with the worst morbidity and mortality.

ECD Treatments

Interferon alfa: Hervier et al²³ studied the efficacy of high dose (≥ 18 million units or ≥ 185 mcgr PEG) vs standard dose (9 million units or 135mcgr PEG) interferon alpha in 24 patients with ECD and stability or improvement was seen in 67% of patients. The severity of the disease was key in patient response to interferon therapy; CNS and heart disease are the most difficult to treat and require high-dose interferon. Remission was partial and recovery was never seen. Prolonged treatment is suggested, up to several years. Treatment may not be tolerated by all patients due to side effects.

Table 1. Results of Interferon Alpha Treatment for ECD

Interferon regimen	Stability	Improvement	Worsening	No data
Low dose : 9M units or 135mcgr PEG	6/24	1/24	5/24	12/24
High dose: ≥ 18M units or ≥ 185mcgr PEG	7/24	11/24	6/24	0/24

Imatinib: Janku et al²⁸ reported the use of imatinib in 3 patients with histiocytosis. Response was seen within weeks of therapy, but the mechanism of action that elicited this response was not determined. The response might be explained by the inhibition of platelet derived growth factor receptor beta (PDGFB), which can be expressed in LCH and ECD histiocytoses and that inhibits the differentiation of CD34 positive cells to dendritic cells. Patients either had disease stability or progression after months of therapy. Recovery was not seen and prolonged treatment is recommended.

